8.4. RANDOMIZATION

A randomization system will be developed by the biostatistician. The objective of randomization is to prevent possible selection bias by providing random treatment assignment to each subject; and to maintain treatment balance with respect to relevant prognostic variables.

Each cohort will start from a permuted block randomization with a block size of 6, including 4 assignments to the AAT arm and 2 assignments to the placebo arm. This initial block of 6 patients will provide information for early safety assessment of AAT.

Following the initial block, additional subjects will continue to be randomized between AAT and placebo in a 2:1 fashion, using random block sizes of 3 and 6.

8.5. BLINDING

The study will be conducted in a double blind manner. Identical study treatment infusion packages will be prepared by our clinical trial coordinator. Study subjects, treating investigators, and efficacy endpoint assessors will be blinded to treatment assignments.

The clinical trial coordinator will produce identical sealed envelopes that contain identification of treatment codes. Prior to initiation of the trial, these envelopes will be stored in a locked file cabinet at the coordinator's office in its limited access central file room.

The DSMB will be partially unblinded for the closed reports (data reported by treatment groups "A" and "B" only). However, if it so wishes, it may be completely unblinded at any time during the trial. If the DSMB wishes to be unblinded on a particular subject only, the NIDDK Liaison to the DSMB should email the request to the unblinded biostatistician.

8.6. MISSING DATA

All efforts will be put forth to ensure near complete follow-up, in particular with the assessment of the primary outcome at 12 months and occurrence of death. Nevertheless, minimal missing data may be inevitable.

As the primary approach, for the primary efficacy analysis with the mITT population, data will be assumed to be missing at random, with no data imputation. Sensitivity analysis with multiple imputations for missing primary endpoints will be conducted to assess whether the findings are consistent across alternative analysis approaches. We plan to use PROC MI and PROC MIANALYZE in the SAS software. A distribution for the primary outcome is derived from a logistic regression model that accounts for covariates assessed at baseline and clinical visits prior to Day 75. A random sample from this distribution is used to impute values for missing primary outcomes. Five sample data sets with complete efficacy endpoint are generated through PROC MI, and each of the data sets are analyzed according to the method described, and the results (regression parameter and covariance matrix estimates) for each sample are combined and analyzed with PROC MIANALYZE to derive a valid statistical inference about the treatment effect.

Missing data in secondary endpoints will be assumed missing at random and no data imputation will be used in secondary endpoints analyses.

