8.2.2. PER-PROTOCOL POPULATION

The per-protocol (PP) population includes all randomized subjects who meet the study eligibility criteria, completed the assigned treatment infusions, and have the primary efficacy endpoint assessed.

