8.7. ASSESSMENT TIME WINDOWS

The Baseline visit should occur within 28 days of the screening visit. For all scheduled visits, allowable visit windows and study procedures are \pm 14 days from the calculated target day. The target day is defined as (Baseline Visit + 75 days) for the Day 75 target day, and (Baseline Visit + 365 days) for the Day 365 target day. If multiple measurements occur within the assessment time window, the measurement closest to the scheduled target day will be analyzed. Data collected outside of the specified time window will not be included in the primary analysis.

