8.9. EFFICACY ANALYSES

The primary efficacy analyses will involve the use a general linear mixed model (GLMM) to test whether the primary endpoints differ over time between subjects assigned to the AAT arm when compared to subjects assigned to placebo. The analysis will be performed on the mITT and PP populations, although the analyses within the mITT population will be considered primary.

Contrasts will be constructed to estimate the AAT treatment effect on outcomes at day 75 and at day 365. To account for the fact that observations within the same subjects will be correlated, various error covariance structures will be considered, including unstructured, autoregressive, and compound symmetry. If model assumptions are not met (e.g. normality) alternative strategies will be utilized, including transformations of dependent variables and non-parametric alternatives. Any pre-transplantation subject characteristics be found to be significantly different between the study subjects and historical controls will be included as covariates for all between-group comparisons. Model fit will be assessed using criteria such as Akaike Information Criterion. All primary and secondary outcomes will be reported in study communications.

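### The only sensitivity analysis for missing primary data keeps the missing-at-random assumption, so it cannot test that assumption, and five imputations are too few for a stable result

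*Combined protocol and SAP*

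**What the plan says.** Section 8.6 sets the primary approach for the mITT population: "data will be assumed to be missing at random, with no data imputation". The only further missing-data analysis of the primary endpoint is this: "Sensitivity analysis with multiple imputations for missing primary endpoints will be conducted to assess whether the findings are consistent across alternative analysis approaches". The distribution used to fill in missing outcomes is "derived from a logistic regression model that accounts for covariates assessed at baseline and clinical visits prior to Day 75". On the number of imputations: "Five sample data sets with complete efficacy endpoint are generated through PROC MI". The results are then combined with PROC MIANALYZE. No random seed is given.

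Three other sections bear on the point.
- Section 8.9 fits a mixed model with contrasts at Day 75 and Day 365, so the primary analysis uses the Day 75 outcome.
- Section 8.2.2 limits the per-protocol set to eligible subjects who "completed the assigned treatment infusions, and have the primary efficacy endpoint assessed".
- Section 8.7 adds a source of missing values: "Data collected outside of the specified time window will not be included in the primary analysis".

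No delta-adjusted, reference-based, tipping-point or other missing-not-at-random (MNAR) analysis appears anywhere in the document.

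**The concern.** A sensitivity analysis for missing data is useful when it relaxes the assumption that the primary analysis cannot verify. Here that assumption is MAR: given the observed data, patients without a Day 365 meal test are taken to have the C-peptide outcome that the model predicts. Section 8.6 does not attach the term MAR to the imputation step. But drawing values from a model on observed covariates, with no departure parameter, implies it. The per-protocol analysis does not fill the gap, because it leaves out everyone whose endpoint is missing.

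If missing patients did worse than predicted, and to a different extent in the two arms, both planned analyses could carry the same bias and still agree. That agreement could then be reported as robustness. The effect estimate matters beyond this trial, because section 8.3 intends it for the design of a larger one.

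Separately, five imputations leave simulation noise in the sensitivity result, and without a fixed seed that result cannot be reproduced.

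**Working it through.** **Inputs.** From the document: 32 AAT and 16 placebo patients (section 3.1), up to 10% loss to follow-up and 80% power for 0.9 SD (section 8.3), five imputations (section 8.6). Assumed: two-sided 5% testing, a split of the loss into 3 AAT and 2 placebo patients, the size of any shift, and, where used, a 20% missing rate.

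**1. The plan's own figure.** With 10% loss, 28.8 and 14.4 patients are evaluable. SE = sqrt(1/28.8 + 1/14.4) = 0.323 SD. Power = Phi(0.9/0.323 - 1.96) = 79.6% by the normal approximation, or 77.7% by the noncentral t. The stated 80% reproduces approximately.

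**2. Yardstick.** With 29 and 14 observed, the 95% CI half-width is t(41) x sqrt(1/29 + 1/14) = 2.02 x 0.325 = 0.66 SD.

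**3. Bias that neither analysis would show.** If missing patients lie a given shift away from their MAR prediction, each arm mean is off by (missing fraction x shift).

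| Missing AAT | Missing placebo | Error in the MAR effect estimate |
|---|---|---|
| 1 SD lower | as predicted | 3/32 = 0.09 SD too high |
| 1 SD lower | 1 SD lower | 3/32 - 2/16 = -0.03 SD (too low) |
| 1 SD lower | 1 SD higher | 3/32 + 2/16 = 0.22 SD too high |

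The first row is about one seventh of the half-width (0.094/0.657) and the third is one third (0.219/0.657).

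**4. Does MAR imputation reveal it?** This simulation used 32 against 16 patients, no true effect, and missing AAT outcomes 1 SD worse than predicted. The full-data effect averaged about -0.09 SD at 10% missing and -0.19 SD at 20%. The observed-data estimate and the five-imputation estimate both averaged about 0. A normal imputation model stood in for the logistic one, because the endpoint is continuous. The Day 75 value was not modelled, so the close agreement seen between the two estimates (correlation 0.99 and 0.98) cannot be carried over to the planned mixed model.

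**5. What a tipping-point run would show.** At 10% missing, an observed p of 0.03 passes 0.05 when missing AAT outcomes are between 0.5 SD (p = 0.046) and 1 SD (p = 0.072) worse than predicted. An observed p of 0.01 reaches 0.05 at about 1.5 SD. At 20% missing, p = 0.03 passes 0.05 between 0.25 and 0.5 SD.

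**6. Seed noise.** As a rough guide, the between-seed SD of the pooled estimate, in SE units, is sqrt(fraction of missing information / m). The simulated fraction is about 0.12 at 10% missing. This gives sqrt(0.12/5) = 0.15 and sqrt(0.12/100) = 0.035. Direct simulation gives 0.13-0.15 at m = 5 and 0.03-0.04 at m = 100. A sensitivity result at t = 2.0 then ranges over 2.0 +/- 1.96 x 0.14, or p from about 0.03 to 0.09 on 41 df. An observed p of 0.03 gives imputation p-values of about 0.014-0.084 across seeds at m = 5 and 0.026-0.038 at m = 100. At an observed p of 0.01, about 99% of seeds stay below 0.05 even with m = 5.

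**The case against.** The case against is substantial, and much of it stands.

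- **The two analyses need not agree.** A reader might infer that the imputation must reproduce the primary result. The document does not support this: the imputation covariates stop before Day 75, while the mixed model uses the Day 75 outcome. In a simulation with 3 AAT dropouts taken from the lowest Day 75 quartile, an analysis ignoring Day 75 differed from one using it by about 0.07, 0.09 and 0.12 SD for assumed Day 75 to Day 365 correlations of 0.5, 0.7 and 0.9. Such a difference reflects conditioning on less information. It is still no test of MAR.
- **The mechanism is not documented.** No section says that patients with failed grafts skip the meal test. Section 2.3.4 treats C-peptide and glucose testing as routine care, section 6.4 lets study visits coincide with routine ones, and section 5.4.2 keeps patients under observation after they stop study drug. Section 8.6 expects little missing data, and 10% is a planning ceiling. Graft failure visible at Day 75 is already conditioned on in the mixed model. So the shifts above are assumptions. Testing such assumptions is the purpose of a sensitivity analysis.
- **Direction.** Poor outcomes among missing patients would plausibly occur in both arms, where the net error is about -0.03 SD. A reader who takes 0.22 SD as the expected bias goes further than the document allows, since that needs opposite shifts by arm.
- **The seed.** A reader might infer that the trial's main p-value depends on a random seed. It does not, because the primary analysis imputes nothing. Section 8.3 also calls all hypothesis testing exploratory.

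**Conclusion.** The point holds in a limited form. The plan's single missing-data sensitivity analysis shares the MAR assumption of the primary analysis, and nothing else in the document tests it. The size is modest at the planned loss. A 1 SD shortfall confined to missing AAT patients overstates the effect by about 0.09 SD, the same shortfall in both arms understates it by about 0.03 SD, and 0.22 SD is the extreme. These figures rest on a 3 and 2 split of the missing patients and on assumed shifts, and they would grow with more missing data, including values lost to the visit window. Five imputations are a minor weakness that affects only a borderline sensitivity p-value. The exploratory status of testing lowers the stakes, but bias of this kind affects the estimate as well as the p-value. The change is worth making because it costs little.

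**What to change.** Keep multiple imputation in section 8.6 and amend it as follows.

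1. Replace the logistic imputation model with one for a continuous outcome. A logistic model cannot be shifted in SD units of the C-peptide AUC, so the next step depends on this.
2. Add a delta-adjusted tipping-point analysis. Vary the shift applied to imputed values separately in each arm, for example in 0.25 SD steps, and report the combination at which the estimate or its interval changes the conclusion.
3. Use about 100 imputations with a prespecified seed.

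Control-based imputation for the AAT arm is optional. We do not suggest giving patients who die the lowest value or worst rank, because that changes the estimand to a composite.

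The cost is a few more lines of code and one more table, with no new data.

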1.1. PROTOCOL SYNOPOSIS

Study Sponsor	NIH/NIDDK	
Investigational Product	Alpha-1 antitrypsin (AAT)	
Indication	Patients with chronic pancreatitis	
Title of Study	AAT Enhances Islet Autograft Survival	
Protocol Date	12/01/15	

OBJECTIVES

Primary objective: To describe and compare the safety and efficacy of treatment with AAT in chronic pancreatitis patients who undergo total pancreatectomy and islet autotransplantation (TP-IAT).

METHODOLOGY

Study Design	Prospective, controlled, double-blind
Treatments	Recipients will receive AAT before and post islet transplantation
Treatment Duration	Recipients will receive a total of 4 weekly infusions of AAT or placebo.
Study Drug and Formulation	Prolastin-C (Grifols)
Dose and Route of Administration	
 • AAT 60 mg/kg (IV) • Placebo- 0.9 % sodium chloride (IV). 
The first dose will be given on the day of islet transplantation before total pancreatectomy (D0), and then on days 7, 14, and 21 days of islet transplantation.

Number Planned	48
Major Inclusion Criteria	
 • Patients scheduled for total pancreatectomy and islet autotransplantation • Age > 18 years • Diabetes free before surgery

Exclusion Criteria	
 • Patients who are under immunosuppression • Patients who have had puestow or frey pancreatic surgery • Patients who have Immunoglobulin A (IgA) deficiency, known antibodies against IgA, or individuals with a history of severe immediate hypersensitivity reactions, including anaphylaxis to Alpha₁-proteinase inhibitor products (allergic to AAT)
Safety	
 • Physical examination, hematology, serum chemistry, urinalysis, vital signs, adverse event (AE) monitoring, and concomitant medications.
Efficacy	Efficacy of AAT therapy during peri-transplant period in chronic pancreatitis patients who undergo TP-IAT as assessed through islet function, onset of diabetes, glycemic control, pain relief and quality of life measurements.
ENDPOINTS	
Primary Endpoint	Area under the curve for the serum C-peptide level during the first 4 hours of an mixed meal tolerance test (MMTT), normalized by the number of islet equivalents (IEQ)/kg at day 365±14 after the transplant.

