3.4. STUDY OBJECTIVE

The objective of this clinical trial is to describe and compare the safety and efficacy of treatment with AAT in chronic pancreatitis patients who undergo TP-IAT.

3.5. STUDY ENDPOINTS:

3.5.1. Primary endpoint:

The primary endpoint will be Area under the curve for the serum C-peptide level during the first 4 hours of a mixed meal tolerance test (MMTT), normalized by the number of islet equivalents (IEQ)/kg at day 365±14 after islet transplant.

3.5.2. Secondary endpoints (measurements will be done at 365±14 days post-transplantation):

- Proportion of insulin-independent patients following IAT.
- Average daily insulin requirement.
- β cell function as assessed by β -score.

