8.10. SAFETY ANALYSES

Study subjects will be asked to report any and all AEs/new symptoms at any time from study enrollment until 52 weeks after study treatment, whether or not they attribute them to the study intervention or procedures. Subjects, who discontinue the study treatment regimen for any reason, including subjects who are treatment failures due to unable to return for some of the treatment injection(s) will be encouraged to attend the remaining visits for assessment of safety, secondary and pharmacokinetic endpoints.

To assess safety in this population, vital signs will be performed at each of the study visits. Additionally, medical history will be collected at screening and baseline and adverse events occurring after start of study therapy will be recorded.

Since the safety endpoints are primarily binary indicators for each subject (e.g. experiencing a particular AE during the 24-weeks post-treatment), their analyses will involve logistic regression models. For certain safety endpoints, it may be more appropriate for them to be analyzed using survival techniques, which are more suitable for time-to-event data than logistic regression. In such circumstances, Cox proportional hazards models will be used to compare treatment arms; however, should the proportionality assumptions not hold, alternative strategies (e.g. stratified analyses) will be used. The safety analyses will be conducted in the Safety Population.

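### Section 8.6 imputes a continuous C-peptide AUC from a logistic regression, which cannot be run as written, and its predictors stop before the Day-75 AUC

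*Combined protocol and SAP*

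**What the plan says.** - **Endpoint.** The synopsis and section 3.5.1 define the primary endpoint as the 4-hour C-peptide AUC from the meal test, "normalized by the number of islet equivalents (IEQ)/kg at day 365±14 after the transplant". Section 8.3 states its power in standard deviation units.
- **Primary analysis.** Section 8.9 uses a "general linear mixed model (GLMM) to test whether the primary endpoints differ over time", and adds: "Contrasts will be constructed to estimate the AAT treatment effect on outcomes at day 75 and at day 365". It allows transformation or a non-parametric method if normality fails. Section 8.6 makes this primary analysis under missing at random, without imputation.
- **Sensitivity analysis.** Section 8.6: "Sensitivity analysis with multiple imputations for missing primary endpoints will be conducted". It gives the source of the imputing distribution in these words: "the primary outcome is derived from a logistic regression model that accounts for covariates assessed at baseline and clinical visits prior to Day 75". Missing values are then drawn from that distribution, and five completed data sets are analysed and combined with PROC MI and PROC MIANALYZE.
- **Logistic regression elsewhere.** Section 8.10 says that the "safety endpoints are primarily binary indicators for each subject" and that "their analyses will involve logistic regression models".
- **Schedule.** Sections 6.3.6 and 6.4.1 and Appendix 1 place the meal test at Days 75 and 365 only.

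**The concern.** There are two faults in the same sentence of section 8.6.

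First, the model does not fit the endpoint. Logistic regression describes the probability of a category. It supplies no distribution from which an AUC can be drawn.

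Second, the predictor list ends before the first meal test. The best candidate predictor of a missing day-365 AUC, the same patient's Day-75 AUC, is therefore left out. The primary mixed model does use it. The two analyses would then rest on different missing-at-random conditions, and they could disagree for that reason alone.

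This is the only analysis in the plan aimed at missing primary data. Left as it is, someone must choose a different imputation model at the analysis stage, which pre-specification is meant to avoid.

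**Working it through.** **1. The plan's own figure.** Section 8.3 gives 32 v 16 subjects, up to 10% loss, an effect of 0.9 SD and 80% power. Two-sided 5% is assumed, because no alpha is stated for this calculation.

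- Completers: 32 × 0.9 = 28.8 and 16 × 0.9 = 14.4. Missing: 48 × 0.10 = 4.8, about 5 subjects.
- SE of the difference = √(1/28.8 + 1/14.4) = 0.323 SD.
- Power = Φ(0.9/0.323 − 1.96) = Φ(0.83) = 0.796.

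The 80% reproduces. It treats the AUC as a continuous mean.

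**2. Can the logistic model be run?** A binary logit fitted to 43 simulated AUC-type values (48 less 5) is rejected, because the outcome lies outside 0 to 1. Treated as a class variable, the outcome has 43 levels for 43 subjects. Neither gives a usable distribution. This result needs no assumption about dropout.

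**3. How many earlier AUC values can the imputation use?** Meal tests are at Days 75 and 365, and predictors stop before Day 75. The imputation model has none; the primary model has one.

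**4. What if only the model type is corrected?** Consider linear-regression imputation on arm alone, with all losses after Day 75. The expected imputed arm mean is the mean of the observed patients. Let ρ be the Day-75 to day-365 correlation, and let dropout be logistic with slope s per SD of Day-75 AUC. With p the dropout probability, the size of the bias in one arm's mean is

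ρ × s × E[p(1 − p)] / (1 − 0.10).

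The documents give neither ρ nor s. Assumed: ρ from 0.4 to 0.8, s = 0.5 or 1.5. With 10% missing in each arm:

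| s | E[p(1 − p)] | s × E[p(1 − p)]/0.9 | Bias in the difference, opposite directions (2ρ × previous column) |
|---|---|---|---|
| 0.5 | 0.0879 | 0.0488 | 0.039 to 0.078 SD |
| 1.5 | 0.0730 | 0.1217 | 0.097 to 0.195 SD |

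If dropout runs in the same direction in both arms and the arms do not differ at Day 75, the two biases cancel. If the arms differ by 0.9 SD at Day 75 and share one dropout intercept, loss rates differ by arm. The bias is then 0.007 to 0.016 SD (s = 0.5) or 0.037 to 0.091 SD (s = 1.5) in the same direction, and 0.037 to 0.083 or 0.084 to 0.223 SD in opposite directions.

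**5. Simulation at the trial's size.** There were 216 settings of 3,000 trials each: 32 v 16, 10% missing, five imputations, baseline-covariate correlation 0 or 0.5, Day-75 effect 0 or 0.9 SD, and all or half of the losses after Day 75. Absolute bias in the difference without the Day-75 AUC:

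| Dropout pattern | s = 0.5 | s = 1.5 |
|---|---|---|
| Unrelated to Day-75 AUC | about 0 | about 0 |
| Same direction, no Day-75 difference | about 0 | about 0 |
| Same direction, 0.9 SD Day-75 difference | up to 0.02 | 0.02 to 0.09 |
| Opposite directions | 0.01 to 0.08 | 0.03 to 0.21 |

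The table is for all losses after Day 75. If half the losses are random and earlier, the maxima fall to 0.01 and 0.06 (same direction) and 0.04 and 0.11 (opposite). With the Day-75 AUC included, and for the primary mixed model, bias stayed within 0.006 SD in every setting. Under random dropout, leaving it out widened the spread of the estimate by 0 to 4%.

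Against the SE: 0.21/0.323 = 0.65 at the extreme; 0.08/0.323 = 0.25 at s = 0.5.

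**The case against.** **The Day-75 limb may be a misreading.** Section 8.9 follows the primary endpoints over time with contrasts at both visits. Predictors measured before the first outcome visit would suit joint imputation of Day 75 and day 365. This is a fair reading, but section 8.6 does not state it, and the synopsis and section 3.5.1 define the primary endpoint at day 365 only. The text needs clarifying in either case.

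**The logistic model may be meant for missingness.** A propensity approach would use one. Section 8.6, however, says that the model gives the distribution of the outcome.

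**The bias figures do not measure the main fault.** This is correct. They describe a partly corrected method and rest on assumed inputs. The largest needs a steep slope, opposite directions by arm and every loss after Day 75. Nothing in the documents points to opposite directions, and patients and treating investigators are blinded.

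**The per-protocol analysis is a second check.** It is limited to subjects with the endpoint assessed and all infusions completed, so it compares completers. It does not address what happened to the missing values.

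**The corrected analysis adds little.** This stands. It would use the same visits and the same missing-at-random assumption as the primary mixed model, so it tests no departure from that assumption.

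**Conclusion.** The concern holds and should be fixed. That the logistic imputation cannot be run follows from the plan's own definitions and needs no assumption. On the plain text, the Day-75 AUC is also left out. If joint imputation was meant, section 8.6 has to say so.

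The consequence is limited. It touches one sensitivity analysis, about 5 of 48 values at the stated maximum loss, in a trial whose section 8.3 calls its testing exploratory. The primary analysis, sample size and power do not change. For a version corrected only in model type, the bias runs from zero to about a quarter of a standard error under mild dropout dependence, and to about two thirds of one in the extreme assumed case.

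**What to change.** In section 8.6:

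- Replace the logistic regression with a continuous-outcome method in PROC MI (linear regression or predictive mean matching), on the scale used in the primary model. Section 8.9 leaves that scale open until assumptions are checked, so say that the imputation follows the final choice.
- List the predictors: treatment arm, the baseline and pre-Day-75 covariates, and the Day-75 AUC.
- Where the Day-75 AUC is also missing, impute it first in the same procedure, then day 365. This also settles whether Day 75 is a predictor or an imputed outcome.
- State that the analysis still assumes missing at random and is expected to agree closely with the primary mixed model.

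The cost is SAP wording and a few lines of code before database lock, with no extra data or patients. The drawback is that the corrected analysis is close to a repeat of the primary one.
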